#### 9.0 REPORT OF ADVERSE EVENTS

Study participants will be told of any possible adverse reactions or side effects from exposure to this method or product. Oral irritation is possible. If side effects occur, it is expected to be mild and temporary. Any event will stop when the study participant stops being exposed to the instrument or returns to their normal oral hygiene. At all examinations, each participant will be asked if they have experienced any discomfort or oral irritation. The investigators will record any and all adverse reactions and report this documentation to the Product Safety Assurance Department. The nature of the reaction and any correlation with product usage will be assessed. If the evidence indicates that the adverse reaction may be due to product usage, the study participant will be instructed to discontinue product use and appropriate treatment will be provided. In the event of an adverse experience, emergency or other problems or questions regarding your participation in this study participants can contact the following investigators:

[name] at [contact] [name] or the Research Oversight and Compliance Office - Human Research Ethics Program at [contact] or [contact] In the event of a medical emergency, please contact your physician

#### 9.1 Definitions

Adverse Events (AEs) and Serious Adverse Events (SAEs) are defined by the ICH Guideline for Good Clinical Practice (ICH GCP) as follows:

Adverse Event: Any untoward medical occurrence in a study participant or clinical investigations study participant administered a pharmaceutical product and which does not necessarily have to have a causal relationship with this treatment. An adverse event (AE) can therefore be any unfavorable and unintended sign (including abnormal laboratory finding), symptom, or disease temporally associated with the use of a medicinal product, whether or not considered related to the medicinal product.

AEs include any clinically significant deterioration of a study participant's medical status, after being enrolled and signing an Informed Consent Form. The AE may involve any organs or systems and can be represented by the new onset or the deterioration of a disease, a syndrome, a symptom, a physical sign, as well as by findings and results of instrumental examinations and laboratory tests. Any medically relevant and untoward change from study enrollment, including frequency or pattern changes for a fluctuating condition (e.g., migraine), occurring after signing an informed consent is an adverse event. All such occurrences must be recorded and reported accordingly, whether they appear causally related to the study medication, or not.

Serious Adverse Event: Any adverse event occurring at any dose that results in any of the following outcomes:

- Death
- Life threatening adverse event
- Instudy participant hospitalization, or prolongation of existing hospitalization
- Persistent or significant disability/incapacity
- Congenital anomaly/birth defect
- Temporary loss of daily function

Important medical events that may not result in death, be life-threatening, or require hospitalization may be considered a serious adverse experience when, based upon appropriate medical judgment, they may jeopardize the study participant or study participant and may require medical or surgical intervention to prevent one of the outcomes listed in this definition.

Examples of such important medical events include allergic bronchospasm requiring intensive treatment in an emergency room or at home, blood dyscrasias or convulsions that do not result in instudy participant hospitalization, or the development of drug dependency or drug abuse.

**IMPORTANT NOTES**: The concepts of Adverse Event / Experience (AE) and Serious Adverse Event / Experience (SAE) represent **regulatory** instruments used to evaluate and monitor the safety of clinical trial study participants. Therefore, these terms only apply in light of their regulatory definition. The term "serious", in a regulatory sense, does not necessarily mean "severe". All adverse events (serious and non-serious) reported during a study will be taken into account when analyzing the study data and establishing the safety profile of the investigational drug, and will be included in the final study report. The SAE concept is primarily used to identify,

during the conduct of the trial, those adverse events that may require an expedited reporting procedure to regulatory authorities.

Death: The outcome of death requires that the AE that resulted in death be reported as an SAE. Death, in and of itself, is not an AE; it is only an outcome. The cause of death is the AE; therefore, the investigator should make every effort to obtain and document the cause of death for all study participants who die during the study. If, despite all efforts, the cause of death remains unknown, the AE it should be documented as "unspecified fatal event".

Life-threatening Adverse Event: Any adverse event that places the study participant or study participant, in the view of the investigator, at immediate risk of death from the reaction as it occurred (*i.e.*, it does not include reaction that had it occurred in a more severe form, might have caused death).

Hospitalization: It should be noted that hospitalization, in and of itself, does not represent an SAE. It is the adverse event leading to the study participant's hospitalization that becomes "serious" when it requires instudy participant care. Consequently, SAE should not be reported in case of pre-planned hospitalizations for pre-existing conditions that did not worsen during the study.

**Disability:** A substantial disruption of a person's ability to conduct normal life functions.

# 9.2 Documenting and Reporting Adverse Events

#### 9.2.1 General Procedures for All Adverse Events

All clinical complaints, symptoms, or signs that meet the adverse event definition will be recorded on the Adverse Reaction Form (Appendix VIII) using a recognized medical term or diagnosis that accurately reflects the event. Source documentation should be maintained that allows for clear identification of each adverse event and the following parameters required for the form:

- AE description
- Date of onset
- Date of resolution
- Outcome
- Severity
- Seriousness
- Relationship to study drug (causality)
- Actions taken

Adverse events will be assessed by the investigator or designee for severity, relationship to the study product, possible etiologies, and whether the event meets the criteria as a serious adverse event and therefore requires immediate notification of the sponsor.

For data collection purposes, the outcome of all adverse events recorded on the Adverse Reaction Form will be designated as of the completion of the final evaluation or examination. However, the investigator is responsible for following all adverse events until resolution or until no longer of clinical concern, and providing these data to the sponsor.

# 9.2.2 Reporting Procedures for Serious Adverse Events

Any adverse event that is serious or potentially serious requires additional detailed reports and follow-up. A serious adverse event must be reported via telephone to the sponsor's representative immediately (within 24 hours) so as to facilitate discussion and implementation of necessary follow-up measures, and to enable the sponsor to submit necessary reports to regulatory authorities and other investigators. Following the initial telephone notification, the investigator must complete and submit a Serious Adverse Event Report Form to the sponsor within one calendar day. Serious Adverse Event

Report Forms will be provided to the investigator upon initiation of the study. Once the sponsor reviews the Serious Adverse Event Report Form, additional information may be requested from the investigator to allow appropriate medical evaluation and determine the regulatory reporting requirements.

The investigator is responsible for following all adverse events, especially those deemed "serious", until resolution or until the event is no longer of clinical concern, and for providing these data to the sponsor in an agreed-upon format. The investigator is also responsible for reporting all serious adverse events to the Institutional Review Board (IRB) overseeing the conduct of the study at the respective study center, according to the rules and procedures established by the IRB.

Safety will be evaluated by oral examinations, clinical laboratory evaluations, descriptive analysis of AEs (including incidence, severity, seriousness, andrelatedness), and immune response, over the entire period of the study.

#### 9.2.3 Reporting Adverse Events to Health Canada

All Adverse Events will be reported to Health Canada as per the Natural Health Product Regulations. This report must be submitted to Health Canada by the researchers no later that 7 days after they have been notified. The online form is available at:

https://www.canada.ca/en/health-canada/services/drugs-health-products/medeffect-canada/adverse-reaction-reporting/natural-health-products.html

#### 10. COMPENSATION

Participants of the study will receive monetary compensation of 1000 CAN\$ after completion of all trial visits. In addition, they will receive 2 professional dental cleaning treatments prior and subsequent to stopping all oral hygiene procedures. They will also receive proper oral hygiene instructions and 3 kits for at-home daily hygiene during the trial.

# 11. QUALITY ASSURANCE/CONDUCT OF THE STUDY

This clinical research study will be conducted in compliance with this protocol and U.S. Federal Regulations governing informed consent (21 CFR 50), Institutional Review Board (21 CFR 56), applicable regulations governing Investigator conduct (21 CFR 312) and/or any local regulatory agency (where applicable).

It is the responsibility of the Investigator to ensure that all study participant data are collected and reported according to the study protocol. Study participant records will indicate study

participant and examination information such as visit dates, examiners, etc. that is unique to this study and the study participants. Proper documentation of all adverse events and final resolutions will be maintained. Case report forms will be used for recording all clinical data. All CRFs used in this study will be provided by the study sponsor. The Investigator will be responsible for maintaining original consent forms, case report forms (CRFs), and other source documentation.

These are examples of case report forms that can be used to collect information/data while conducting this study:

- Study participant Assignment Log (Randomization chart)
- Demographic Log
- Inclusion/Exclusion Criteria Form
- Continuance Criteria
- Adverse Event Form
- Oral Hard & Soft Tissue Exam Form

Forms may be added or deleted, if deemed necessary, by agreement between the PI (principal investigator) and study sponsor prior to the study start date.

#### 12. DATA MANAGEMENT RESPONSIBILITIES

Data collection is the responsibility of the clinical research site staff under the direction of the Principle Investigator. The Investigator will keep a copy of every document (clinical and laboratory) related to the research study.

Data generated at the clinical site will be transferred to the sponsor by the Principal Investigator via mail or electronic email for statistical analyses. The principal Investigator and study manager are responsible for the review and interpretation of the analyzed data.

# 12.2 Study participant Termination/Procedures

A genuine effort will be made to determine the reason(s) why a study participant fails to return for the necessary visit(s) or is dropped from the study. Study participants could be dropped from the study if any of the following occur:

- 1. Study participant fails to substantially comply with the protocol requirements.
- 2. Study participant fails to report for a scheduled examination.
- 3. Study participant is treated with medications during the course of the study, which may interfere with the parameters of the study.
- 4. Study participant develops an adverse reaction. The study Investigator will immediately notify the study monitor and information will be recorded on Adverse Reaction Form.
- 5. Study participant receives emergency dental or medical treatment, which may interfere with the parameters of the study.
- 6. Sponsor elects to terminate the study.
- 7. Study participant elects to terminate participation in the study.

# 12.3 Removal of Study participants From Study

Study participants will be dropped from the study if they receive emergency dental treatment, which in the opinion of the monitor could influence the parameters of the study. Any study participant treated with an antibiotic during the study will be dropped from the study. Either the investigator or the sponsor may terminate the study at any time for well

documented reasons, provided written notice is submitted at a reasonable time in advance of the intended termination.

# 12.4 Pregnancy

No pregnant women will intentionally be enrolled in this study. All female study participants being considered for this study will be screened with a urine pregnancy test before the start of the trial. All enrolled female study participants will be required to report to the clinical/research investigator if they become pregnant during the course of the 9-week study. In the event a woman enrolled in this clinical research study becomes pregnant at any time during this study, participation in this study will be terminated upon the clinical staff's notification of the event. The study participant's medical records used in this study will be updated to reflect the pregnancy and there will be follow-up contact until the end of the pregnancy to record the outcome in the clinical file.

# 12.5 Ethical and Regulatory Requirements/Human Study participant Protection

Participants may opt out of the study at any time and request the destruction of all stored samples. Sample destruction and disposal will be completed and properly documented by Coriell. All samples and data will be relayed to researchers in the absence of identifying information; therefore, no personal information or results will be relayed back to participants. The testing done in this study is for research purposes only and not intended to make any medical diagnosis.

# 12.6 Protocol Approval, Study Monitoring and Compliance

Prior to initiation of the study, the Investigator will obtain approval from the UofT Health Sciences Research Ethics Board for the study protocol, the informed consent document, study instructions, and any forms of advertising in compliance with regulations. The reviewers will also review any change(s) in the protocol before the change is initiated.

#### 12.7 Adherence to Protocol/Amendment(s)

The Investigator will be required to adhere to the final protocol. Any changes to the protocol, except those necessary to eliminate apparent hazards, will require prior approval by the local reviewers through the submission of a protocol amendment. These changes to the protocol must be implemented only through formal written protocol amendments and only upon joint approval by the sponsor and investigator. If a protocol amendment requires changes to the informed consent form, the revised consent form must also be approved by any local board.

Departures from eligibility requirements may be allowed on a case-by-case basis by the medical monitor or other authorized sponsor representative. Such departures must be medically and scientifically justified, must be pre-authorized, and must be documented in the case report form and tracked as official eligibility waivers.

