#### 4.4 Exclusion Criteria:

1) Presence of orthodontic bands.

- 2) Presence of partial or full dentures.
- 3) Tumour(s) of the soft or the hard tissues of the oral cavity.
- 4) Cavitated carious lesions requiring immediate restorative treatment.
- 5) History of allergy to a consumer or personal care products or dentifrice ingredients as determined by the dental profession monitoring the study.
- 6) Participation in any other clinical study or test panel within one month before entering the study.
- 7) Medical condition which requires pre-medication before dental visits/procedures
- 8) Current use of anti-inflammatory, antibiotics, or antimicrobial drugs or within the last 30 days of enrolment.
- 9) History of periodontal disease.
- 10) History of systemic inflammatory, immune conditions and immunocompromised conditions
- 11) Pregnant or nursing women or those planning to get pregnant
- 12) Use of tobacco products.
- 13) Long-term antibiotic or anti-inflammatory therapy.
- 14) Medication or Natural Health Products (NHPs) that could affect the gingiva like calcium channel blockers, anti-epileptic therapy etc.
- 15) Medical condition or any current usage of medication that the investigator considers may compromise the study participant's safety as well as the quality of the study results
- 16) Allergy to any of the following ingredients: Streptococcus Salivarius, Sorbitol, Isomalt, Calcium phosphate dibasic, Potato starch, Mint, Glyceryl dibehenate, Stevia, Maltodextrin
- 17) Use of other probiotics
- 18) Taking anticoagulant medications and those suffering from blood and bleeding disorders
- 19) Recently experienced or will be experiencing dental, oral or any type of surgery.
- 20) Use of anti-plaque/ anti-gingivitis products
- 21) Presence of active infections
- 22) Participants who are experiencing nausea, fever, vomiting, bloody diarrhoe or severe abdominal pain.
- 23) Use of any antibiotics.

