#### 4.5 Continuing Criteria

Each study participant must meet continuance criteria at each visit in order to continue in the study. Study participants will be released from further participation for the following reasons:

- use of non-study dentifrice during treatment periods (acceptable dentifrice will be provided during the study)
- use of oral care products (other than those permitted) during the treatment periods including mouth rinse products and chewing gum.
- non-compliance with study procedures
- actively participating in another clinical study unless permission has been granted by the Principal Investigator
- development of a medical condition or taking a medication which would affect the study outcome (such as an antibiotic) as detailed in the exclusion criteria.
- Subject fails to substantially comply with the protocol requirements.
- Subject fails to report for a scheduled examination.

- Subject is treated with medications during the course of the study, which may interfere with the parameters of the study.
- Subject develops an adverse reaction. The study Investigator will immediately notify the study monitor and information will be recorded on Adverse Reaction Form.
- Subject receives emergency dental or medical treatment, which may interfere with the parameters of the study.
- · Sponsor elects to terminate the study.
- Subject elects to terminate participation in the study. No pregnant women will intentionally
  be enrolled in this study. All female subjects being considered for this study will be asked
  about their pregnancy status. the clinical/research investigator if they become pregnant
  during the course of the 9-week study. In the event a woman enrolled in this clinical
  research study becomes pregnant at any time during this study, participation in this study
  will be terminated upon the clinical staff's notification of the event.

•

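### Section 12.7 allows case-by-case eligibility waivers by the sponsor side with no criterion reserved, which fits badly with its own amendment rule and leaves the periodontal-health and key safety criteria unprotected

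*Protocol*

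**What the plan says.** Protocol section 12.7 has two paragraphs. The first sets a strict rule: "The Investigator will be required to adhere to the final protocol", and "Any changes to the protocol, except those necessary to eliminate apparent hazards, will require prior approval by the local reviewers". It adds that changes are made only by formal written amendment, approved jointly by sponsor and investigator.

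The second paragraph sets up eligibility waivers: "Departures from eligibility requirements may be allowed on a case-by-case basis by the medical monitor or other authorized sponsor representative". It attaches conditions: "Such departures must be medically and scientifically justified, must be pre-authorized, and must be documented in the case report form". Waivers are also to be tracked.

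Section 12.6 says of the ethics reviewers: "The reviewers will also review any change(s) in the protocol before the change is initiated". Section 12.8 gives the board review of significant protocol changes. Neither section mentions a waiver for an individual. Section 4.2 describes the sixty enrolled volunteers as people who qualify, and section 6.1 randomises participants who qualify.

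**The concern.** The trial induces gingivitis in volunteers who start healthy. They go 21 days without oral hygiene (section 6.6), and the aim is prevention (section 2). Inclusion criteria 3 to 6 define that healthy start: little gingival inflammation, shallow probing depths, no attachment loss and no periodontal history. Exclusions such as 10 ("History of systemic inflammatory, immune conditions and immunocompromised conditions"), 16 (allergy to the organism or an excipient) and 18 (anticoagulants and bleeding disorders) protect people who take a live organism and are probed at every visit.

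The waiver clause reaches all of these, and the people who may use it sit on the sponsor side. If a health criterion is waived, the trial partly studies people with existing disease, and prevention becomes mixed with treatment. If a safety exclusion is waived, a volunteer loses a protection in a trial they do not need for their own care.

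**Working it through.** The protocol gives no figure to reproduce, so the check compares passages.

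**Step 1: the two paragraphs of 12.7.**

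| | Protocol change | Eligibility waiver |
|---|---|---|
| Who decides | Sponsor and investigator jointly, after local reviewers approve | Medical monitor or another person authorised by the sponsor |
| Reviewer step | Required, except to remove an apparent hazard | None named |
| Investigator's approval | Required | None named |
| Limit on scope | Full amendment process | No criterion reserved, no cap |
| Record | Written amendment | Case report form, tracked as a waiver |

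There are two possible readings. If a waiver is not a protocol change, it can go ahead with none of the approvals in the left column. If it is a protocol change, the second paragraph permits what the first forbids. Either way the text needs correcting.

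**Step 2: who is enrolled.** Sections 4.2 and 6.1 enrol and randomise people who qualify. A person admitted by waiver fails at least one criterion, and these sections make no provision for such a person.

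**Step 3: which criteria have protection elsewhere.** Sections 4.3 and 4.4 list 10 inclusion and 23 exclusion criteria. Taken alone, 12.7 covers all 33. Other sections narrow this:

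- Pregnancy (exclusion 11): sections 4.5 and 12.4 separately rule out intentional enrolment.
- Interfering medication or products (such as exclusions 8, 17 and 20): section 4.6, Concomitant Therapy, makes the investigator responsible for disqualifying users at screening. Section 12.3 drops anyone treated with an antibiotic during the study.
- Gingival and periodontal health (inclusion 3 to 6): no separate bar at entry. Exclusion 9 repeats the history criterion, but it is itself an eligibility requirement.
- Immune conditions, product allergy, bleeding disorders (exclusions 10, 16 and 18): no comparable separate bar at entry. Anticoagulant use could fall under 4.6 if the investigator thinks it would obscure the results; a bleeding disorder would not.
- Investigator's judgement on safety (exclusion 15): this sits inside 4.4, so 12.7 reaches it too.

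**Step 4: scale.** Planned enrolment is 60 (section 4.2). One waived entrant is 1/60 = 1.7% of the trial. If the arms are 30 each, which is an assumption because the allocation ratio is not stated, that person is 1/30 = 3.3% of an arm. These are shares of one person and not estimates of bias. The protocol gives no expected number of waivers.

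**The case against.** The strongest reply is that the clause is controlled. A waiver needs medical and scientific justification and prior authorisation, and it leaves a record. Admitting someone allergic to the product could hardly meet that test. The ethics board also approves the protocol, including this clause, before the study starts, and a single documented departure need not count as a change to the protocol. The conditions are real and any criticism must state them. They make waivers traceable, but they do not limit which criteria can be waived or bring in anyone outside the sponsor side. That waivers bypass ethics review is an inference from silence, supported by the contrast within one section.

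The effect on the prevention question could also be small. Inclusion 3 already tolerates signs of inflammation at just under 10% of sites. Everyone receives a cleaning and then 14 days of home hygiene before induction. Nothing suggests that waivers would differ between arms. This stands as a reason not to claim a bias of any given size.

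A reader might infer three stronger points that the documents do not support:

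- That all 33 criteria are open in practice. Step 3 shows that pregnancy and interfering products are limited elsewhere.
- That section 4.5 conflicts with exclusion 6. The exclusion concerns "Participation in any other clinical study or test panel within one month before entering the study". The 4.5 clause concerns people already enrolled who are "actively participating in another clinical study unless permission has been granted by the Principal Investigator". They cover different periods, so both can hold, and neither needs an edit on this account.
- That the sponsor would use waivers to fill the trial. The text gives no such motive and names the medical monitor first.

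**Conclusion.** The point holds in a limited form. Section 12.7 contains an operative waiver rule that reserves no criterion, sets no cap and names no approval by the investigator or ethics board. It fits badly with the adherence and amendment rule just before it, with 12.6, and with the qualifying participants of 4.2 and 6.1. The exposure that matters is inclusion 3 to 6 and safety exclusions such as 10, 16 and 18, which have no comparable protection elsewhere at entry.

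This concerns governance and the definition of the study population. Its effect on the results cannot be computed, since it depends on how many waivers are granted and for which criteria. The conclusion assumes that eligibility requirements in 12.7 means the lists in 4.3 and 4.4, and that the absence of a reviewer step is to be taken as written. It is a cheap improvement worth making; it does not show that the design is invalid.

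**What to change.** Delete the waiver paragraph in section 12.7 and put in its place: *No eligibility waivers will be granted. A criterion that proves unworkable will be changed for all participants by an approved amendment. Anyone found ineligible after randomisation will be recorded as a protocol deviation.*

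This brings 12.7 into line with its own first paragraph and with 4.2, 6.1 and 12.6. It needs no new data, visits or participants. The cost is a few more screen failures or an occasional amendment.

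A milder alternative would keep the clause, list the criteria that cannot be waived and require ethics-board notification. That would meet part of the concern, but people outside the stated population could still be randomised.
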